11.5. Appendix 5: Derived and Transformed Data

11.5.1. Study Population

Demographics
Age

 GSK standard IDSL algorithms will be used for calculating age where birth date will be imputed as follows: 
 Any subject with a missing day will have this imputed as day '15'. Any subject with a missing date and month will have this imputed as '30th June'. Birth date will be presented in listings as 'YYYY'.
Body Mass Index (BMI)

 Calculated as $\text{Weight (kg)} / [\text{Height (m)}]^2$

11.5.2. Date of Completion and Withdrawal

This study only has one on-treatment visit. Subjects either complete or withdraw on the day. There is no follow up visit.

11.5.3. Critical and Overall Errors

Critical and Overall errors

An ordinal variable (error) will be derived to indicate where a participant had any error, or any critical error whilst demonstrating correct device use. If the subject has an overall/critical error the error=Y whilst if they did not have an overall/critical error then error=N. The variables errty/errtycd will be used to determine whether the variable error is referring to a critical or overall error.

An ordinal variable (err_ord) will be derived to indicate the responses of critical error based on comparing responses for the device sequences used. This variable will be used in the sensitivity analysis for critical error data.

If the sequence of inhaler use is ELLIPTA in the 1st period and DISKUS + HandiHaler or Turbuhaler + HandiHaler in the 2nd period, then for critical error in relation to sequence:
 
 err_ord = -1, if subject had critical error in the 1st period but NOT in the 2nd period err_ord = 1, if subject had critical error in the 2nd period but NOT in the 1st period err_ord = 0, if subject had critical errors in BOTH periods or had NO critical errors in BOTH periods

If the sequence of inhaler use is and DISKUS + HandiHaler or Turbuhaler + HandiHaler in the 1st period and ELLIPTA in the 2nd period, then for each preference question:
 
 err_ord = 1, if subject had critical error in the 1st period but NOT in the 2nd period err_ord = -1, if subject had critical error in the 2nd period but NOT in the 1st period err_ord = 0, if subject had critical errors in BOTH periods or had NO critical errors in BOTH periods

The above method also applies to overall errors.

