7.1.2. Planned Efficacy Statistical Analyses

Primary Statistical Analyses
Endpoint(s)

 • Percentage of subjects making at least one critical error after reading the PIL(s)
Model Specification

 • The primary endpoint of the percentage of subjects making at least one critical error after reading the PIL(s) will be analysed using the Intent-to-treat population. • This endpoint will be analysed using conditional logistic regression with subject as fixed strata, and treatment option and period as fixed effects. • Country will be included in the model providing there are sufficient subjects distributed to enable the model to run. If the model will not run with country in the model then country will be removed from the model.
Model Checking & Diagnostics

 • Refer to Appendix 9: Model Checking and Diagnostics for Statistical Analyses.
Model Results Presentation

 • The odds ratio, 95% CI and p-value will be presented for the comparison between treatment options. It will be based on a two-sided hypothesis testing approach of superiority.
SAS Code

 • Logistic regression will be used to calculate the odds ratio with 95% CI and p-value. The following SAS code will be used: <pre> proc logistic data=errors; class device period country; strata subject; model error = country device period / expb; oddsratio device; run; </pre> 
error is derived as shown in Section 11.5.3

Sensitivity and Supportive Statistical Analyses

- A sensitivity analysis will be performed using the Cochran-Mantel-Haenszel (CMH) test. The CMH test serves as a stratified approximation to the Mainland-Gart test, a variation of a one-sample chi-square test that accounts for study inhaler sequence (period). A subject who had an error with both devices or who had no errors with both devices does not provide any information about the superiority of either device. Only those subjects who had error(s) in one device and had no error in the other device are counted for in the Mainland-Gart test.
- SAS code for the CMH test is provided below:

```
proc freq data=errors (where=(err_ord^=0));
    tables seq*err_ord/cmh;
run;
```

As with the main analysis, country will be included as a covariate if sufficient data is available as described above. err_ord is derived as shown in Section [11.5.3](#)

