11.5.4. Responses to Preference Questions

Preference Questions

An ordinal variable (pref_ord) will be derived to indicate the responses to preference based on the sequence of inhaler use. This variable will be used in the statistical analysis for preference data.

If the sequence of inhaler use is ELLIPTA in the 1st period and DISKUS + HandiHaler or Turbuhaler + HandiHaler in the 2nd period, then for each preference question:

- pref_ord = -1, if subject prefer ELLIPTA
- pref_ord = 1, if subject prefer DISKUS + HandiHaler or Turbuhaler + HandiHaler
- pref_ord = 0, if subject has no preference

If the sequence of inhaler use is DISKUS + HandiHaler or Turbuhaler + HandiHaler in 1st period and ELLIPTA in 2nd period, then for each preference question:

- pref_ord = 1, if subject prefer ELLIPTA
- pref_ord = -1, if subject prefer DISKUS + HandiHaler or Turbuhaler + HandiHaler
- pref_ord = 0, if subject has no preference

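### The sensitivity variable err_ord is coded by device, so the planned CMH test of the primary endpoint tests the period effect and not the device difference

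*SAP*

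**What the plan says.** SAP 7.1.2 specifies a CMH test as the sensitivity analysis of the primary endpoint. It explains the test this way: "The CMH test serves as a stratified approximation to the Mainland-Gart test, a variation of a one-sample chi-square test that accounts for study inhaler sequence". It adds that only subjects with an error on one option and not the other tell us anything about device superiority. The code drops the concordant subjects and requests "tables seq*err_ord/cmh".

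SAP 11.5.3 derives err_ord. In the ELLIPTA-first block: "err_ord = -1, if subject had critical error in the 1st period but NOT in the 2nd period" and "err_ord = 1, if subject had critical error in the 2nd period but NOT in the 1st period". In the comparator-first block the signs are reversed: +1 for an error in period 1 only, -1 for an error in period 2 only. The section ends: "The above method also applies to overall errors". SAP 8.1.2.2 asks for the same sensitivity analysis of overall errors, and Table 2.10 (shell EFF_T07) reports both.

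SAP 11.5.4 derives pref_ord for a CMH test of the same form. In its ELLIPTA-first block, "pref_ord = 1, if subject prefer DISKUS + HandiHaler or Turbuhaler + HandiHaler"; in its comparator-first block the same preference is scored -1.

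**The concern.** A Mainland-Gart test compares the two sequences on when the error occurred, first or second period. The code therefore has to mean the same period in both sequences. The signs in SAP 11.5.3 flip between sequences in a way that makes the code mean the same device instead. pref_ord does what the test needs; err_ord does not.

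At stake is the only check on the primary endpoint that uses a different method. A real ELLIPTA advantage would probably be accompanied by a non-significant sensitivity p-value. A learning effect between periods could produce a significant one with no device difference. Such an effect is plausible: both options are tested at one visit, instruction is given in period 1 to anyone who makes an error, and the checklists in Protocol Appendix 2 share several steps across inhalers. Shell EFF_T07 prints this p-value directly below the error counts for each device, so it would be read as a device comparison.

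**Working it through.** **Inputs.** Protocol 10.2: 72 subjects per sub-study, two-sided 5%, rate pairs (ELLIPTA/comparator) 11/37, 10/35, 9/34, 8/32, 7/31 and 6/29%. Protocol 7.2: equal allocation, so 36 per treatment order. SAP 11.8.1: sequence has two levels. The documents give neither the within-subject correlation of errors nor a period effect; both are taken as 0 and then varied.

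**The plan's own figure.** Protocol 10.2 states at least 90% power for the conditional logistic regression. Simulation (200,000 trials per scenario) gives 96.1% to 97.1% for the likelihood-ratio test with treatment and period, and 92.1% to 95.5% for a treatment-only Wald test. The Wald test with treatment and period gives 93.5% to 95.0% among estimable data sets. (If fits with an empty discordant cell count as failures, that last figure is 58.5% to 81.2%; this has no bearing on err_ord.) The stated power is reproduced, so the same set-up can be used for the CMH test.

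**What err_ord means.**

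| Sequence | Error only on | Period | err_ord as written | Coded by period |
|---|---|---|---|---|
| ELLIPTA first | ELLIPTA | 1 | -1 | -1 |
| ELLIPTA first | Comparator | 2 | +1 | +1 |
| Comparator first | Comparator | 1 | +1 | -1 |
| Comparator first | ELLIPTA | 2 | -1 | +1 |

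**What the test compares.** Let δ be the log odds ratio for comparator v ELLIPTA and π that for period 2 v period 1. Among discordant subjects the subject effect cancels, and the log odds of err_ord = +1 are:

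- as written: δ + π (ELLIPTA first) and δ - π (comparator first); the difference is 2π, so the device effect drops out;
- coded by period: δ + π and π - δ; the difference is 2δ, so the period effect drops out.

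**A worked table.** At 11/37% the expected discordant counts per order are 36 × 0.11 × 0.63 = 2.5 on ELLIPTA only and 36 × 0.37 × 0.89 = 11.9 on the comparator only. Take 3 and 12 in each order. For a 2×2 table, CMH = (N - 1)(ad - bc)² / (r₁r₂c₁c₂).

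- As written, rows (3, 12) and (3, 12): ad - bc = 36 - 36 = 0, chi-square 0.00, p = 1.00.
- By period, rows (3, 12) and (12, 3): 29 × (9 - 144)² / 15⁴ = 528,525 / 50,625 = 10.44, p = 0.0012.

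A slightly unequal split, (2, 12) and (3, 12), gives 28 × 144 / 25,200 = 0.16 (p = 0.69) as written and 28 × 19,044 / 44,100 = 12.09 (p = 0.0005) by period.

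**Rejection rates of the CMH test.**

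| Scenario | As written | By period |
|---|---|---|
| Six planning pairs, no period effect | 3.0–4.3% | 95.5–96.6% |
| 5% v 60%, no period effect | 0.6% | 100% |
| 11/37%, correlation -0.1 to 0.2 | 2.7–4.6% | 94.4–98.7% |
| 11/37%, period effect -1 logit | 41.1% | 84.5% |
| 24% on both, period effect 0 | 4.9% | 4.9% |
| 24% on both, -0.5 logit | 21.1% | 4.9% |
| 24% on both, -1 logit | 56.9% | 4.7% |
| 24% on both, -1.5 logit | 83.5% | 3.7% |

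The as-written column responds to period and not to device; the by-period column does the opposite.

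**The case against.** The primary inference does not depend on err_ord. The conditional logistic regression uses a separate variable, adjusts for period and carries the sample size; nothing in either document makes success depend on the CMH test. This stands, and it limits the harm to a misleading supportive p-value.

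The mistake would also be partly visible, because shells EFF_T06 and EFF_T07 print the discordant split by device. A split of 24 v 5 beside p = 0.69 would raise a question. That may help someone notice, but the printed p-value would still answer the wrong question.

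SAP 11.8.1 also mentions country in a sensitivity analysis, so the CMH test is not strictly the only one. However, a country main effect is constant within a subject and drops out of the conditional model, so it gives no independent check.

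Saying the test has no power needs a qualifier: with a period effect it does reject when the devices differ (41.1% at -1 logit), but because of period. The false-positive rate likewise depends on an assumed period effect, which is why a range is shown.

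Finally, this may be a drafting slip that a programmer would catch; the comparator-first block of 11.5.3 still refers to preference questions. The program is not available to check, and the SAP text is what a programmer is told to follow.

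**Conclusion.** The concern holds, and the text should be corrected before database freeze. As written, the sensitivity analysis of critical errors, and by extension of overall errors, tests for a period effect. Without a period effect it rejects at or below 5% however large the device difference, where the intended test would reject in about 96% of trials at the planning rates. With a period effect and no device difference, false rejection rises from 21.1% at -0.5 logit to 83.5% at -1.5 logit.

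The algebra and the worked tables follow from the SAP text alone. The rejection rates assume 36 subjects per order and, except where varied, independent errors. If sequence were entered with four levels instead of two, the test would still compare device-coded proportions between sequences, and the defect would remain.

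**What to change.** In the comparator-first block of SAP 11.5.3, swap the two signs: err_ord = -1 for an error in the first period only and +1 for an error in the second period only, for critical and overall errors alike. Remove the stray reference to preference questions there. Leave the table request in 7.1.2 as it is, and state that sequence has two levels. If the test is to be adjusted for country, as the EFF_T07 footnote says, request `country*seq*err_ord`, the stratified form that SAP Appendix 9 already uses for preference.

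Keeping the device code and comparing devices directly is possible, but a simple comparison of the discordant counts would give up the adjustment for period that the SAP wants, so the sign swap is better.

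The cost is two lines of derivation text and the matching program lines. Data collection, sample size and the primary analysis do not change.

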11.5.4. Responses to Preference Questions

Preference Questions

An ordinal variable (pref_ord) will be derived to indicate the responses to preference based on the sequence of inhaler use. This variable will be used in the statistical analysis for preference data.

If the sequence of inhaler use is ELLIPTA in the 1st period and DISKUS + HandiHaler or Turbuhaler + HandiHaler in the 2nd period, then for each preference question:

- pref_ord = -1, if subject prefer ELLIPTA
- pref_ord = 1, if subject prefer DISKUS + HandiHaler or Turbuhaler + HandiHaler
- pref_ord = 0, if subject has no preference

If the sequence of inhaler use is DISKUS + HandiHaler or Turbuhaler + HandiHaler in 1st period and ELLIPTA in 2nd period, then for each preference question:

- pref_ord = 1, if subject prefer ELLIPTA
- pref_ord = -1, if subject prefer DISKUS + HandiHaler or Turbuhaler + HandiHaler
- pref_ord = 0, if subject has no preference

11.5.5. Number of instructions

Number of Instructions

The number of instructions from the HCP which are needed to demonstrate adequate inhalation technique for each inhaler will be summarised. The number of instruction from the HCP will be assigned as follows:

- NUMINSTR = 0, if no instruction needed correct after reading leaflet
- NUMINSTR = 1, if the participant received 1st instruction and had no error
- NUMINSTR = 2, if the participant received the 2nd instruction and had no error
- NUMINSTR = 3, if the participant received 2nd instruction and had at least one error

From this an ordinal variable (diffinst) will be derived to indicate the difference between the number of instructions required to demonstrate correct use on the ELLIPTA device compared to the DISKUS + HandiHaler or Turbuhaler + HandiHaler devices.

11.6. Appendix 6: Premature Withdrawals & Handling of Missing Data

11.6.1. Premature Withdrawals

Element	Reporting Detail
General	
 • For reporting purposes, subject study completion will be defined as completion of all three periods (both devices and answered questionnaire) on the day of study visit. • Withdrawn subjects will be defined as those who used at least one device but did not complete all assessments. • Withdrawn subjects will not be replaced in the study. • All available data from subjects who were withdrawn from the study will be listed and all available scheduled data will be included in summary tables and figures, unless otherwise specified.

11.6.2. Handling of Missing Data

Element	Reporting Detail
General	
 • Missing data occurs when any requested data is not provided, leading to blank fields on the collection instrument : 
 ○ These data will be indicated by the use of a “blank” in subject listing displays. Unless all data for a specific visit are missing in which case the data is excluded from the table. ○ Answers such as “Not applicable” and “Not evaluable” are not considered to be missing data and should be displayed as such. • As subjects need to be assessed for critical errors on both devices in order for the analysis to be performed, if they only complete one period they will not be included in the analysis. Subjects who complete both devices, but do not answer the questionnaire will be included in all analysis excluding those related to preference.
Outliers	
 • Whilst outliers are not anticipated within this study any subjects excluded from the summaries and/or statistical analyses will be documented along with the reason for exclusion in the clinical study report. Any potential exclusions would be for exploratory purposes only and not for the primary analysis.

11.6.2.1. Handling of Missing/Partial Dates

Element	Reporting Detail
General	
 • Partial dates will be displayed as captured in subject listing displays.
Adverse Events	
 • The eCRF allows for the possibility of partial dates (i.e., only month and year) to be recorded for AE start and end dates; that is, the day of the month may be missing. In such a case, the following conventions will be applied for calculating the time to onset and the duration of the event: 
 ○ Missing Start Day: First of the month will be used unless this is before the start date of study treatment; in this case the study treatment start date will be used and hence the event is considered On-treatment as per Appendix 3: Treatment Phases. ○ Missing Stop Day: Last day of the month will be used, unless this is after the stop date of study treatment; in this case the study treatment stop date will be used. • Completely missing start or end dates will remain missing, with no imputation applied. Consequently, time to onset and duration of such events will be missing. • Start or end dates which are completely missing (i.e. no year specified) will remain missing, with no imputation applied.
Concomitant Medications	
 • Partial dates for any concomitant medications recorded in the eCRF will be imputed using the following convention: 
 ○ If the partial date is a start date, a '01' will be used for the day and 'Jan' will be used for the month ○ If the partial date is a stop date, a '28/29/30/31' will be used for the day (dependent on the month and year) and 'Dec' will be used for the month. • The recorded partial date will be displayed in listings.
Adverse Events	
 • Any partial dates for adverse events will be raised to data management. If the full date cannot be ascertained, the following assumptions will be made: 
 ○ If the partial date is a start date, a '01' will be used for the day and 'Jan' will be used for the month. ○ However, if these results in a date prior to Week 1 Day 1 and the event could possibly have occurred during treatment from the partial information, then the Week 1 Day 1 date will be assumed to be the start date. ○ The AE will then be considered to start on-treatment (worst case). ○ If the partial date is a stop date, a '28/29/30/31' will be used for the day (dependent on the month and year) and 'Dec' will be used for the month. • The recorded partial date will be displayed in listings.

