9.2.3. Follow-up of AEs and SAEs

After the initial AE/SAE report, the investigator is required to proactively follow each participant at subsequent visits/contacts. All SAEs, will be followed until the event is resolved, stabilized, otherwise explained, or the participant is lost to follow-up). Further information on follow-up procedures is given in Appendix 5.

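### Two unreconciled SAP rules cover adverse event dates with a missing day; they give different durations and phases, and one misplaces dates because treatment lasts a single day

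*SAP*

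**What the plan says.** The table in SAP 11.6.2.1 has two rows labelled Adverse Events.

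**Row 1** covers AE dates with month and year but no day: "the following conventions will be applied for calculating the time to onset and the duration of the event". For a missing start day, "First of the month will be used unless this is before the start date of study treatment"; otherwise the treatment start date is used and "hence the event is considered On-treatment as per Appendix 3: Treatment Phases". For a missing stop day, "Last day of the month will be used, unless this is after the stop date of study treatment", in which case the treatment stop date is used. Row 1 also says that completely missing dates are not imputed.

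**Row 2** covers every partial AE date: "Any partial dates for adverse events will be raised to data management". If the query fails, a partial start takes day 01 and month January, and a partial stop takes the last day of the month and December. The start moves to Week 1 Day 1 only "if these results in a date prior to Week 1 Day 1 and the event could possibly have occurred during treatment". The stop has no cap.

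Nothing says which row governs. SAP 11.5.2 states that there is only one on-treatment visit. SAP Appendix 3 defines phase by the Visit 1 date: before it is pre-study, on it is during-study, after it is post-study. Under Protocol 9.2.1, SAEs are collected from consent and other AEs from randomisation. The Schedule of Activities allows up to 30 days from consent to Visit 1. On follow-up, Protocol 9.2.3 says: "All SAEs, will be followed until the event is resolved, stabilized, otherwise explained".

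**The concern.** Row 1 reads like a rule for a trial with a treatment period of weeks or months, where capping a stop date at the end of treatment or flooring a start date at its beginning moves a date only a little. Here both limits are the same day. The cap then removes all follow-up time from an event whose stop day is missing. The floor turns an event that began before Visit 1 into one that began on it. Row 2 covers the same cases and gives other answers.

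At stake are any derived duration or time to onset, and the outputs that depend on phase, such as SAP tables 3.02 (on-study AEs), 3.03 (post-study AEs) and 3.05 (on-treatment AEs leading to discontinuation or withdrawal). As written, the result depends on which row the programmer picks.

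**Working it through.** The plan states no figure to reproduce. The check applies each rule as written, with V for the Visit 1 date and treatment start = treatment stop = V (SAP 11.5.2).

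**General result for row 1**

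- Stop day missing: imputed stop = min(last day of recorded month, V). If the recorded month is the month of V or later, its last day is on or after V, so the result is always V.
- Start day missing: imputed start = max(first day of recorded month, V). If the recorded month is before the month of V, its first day is before V, so the result is always V, labelled On-treatment. Nothing checks whether onset on V was possible.

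Running the rules over all 365 possible Visit 1 dates in a year confirms this. The stop was V in 2,190 of 2,190 cases (365 × 6 stop months) and the start was V in 1,095 of 1,095 (365 × 3 earlier start months). Row 2, with the recorded month kept, left the start before V in all 1,095.

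**Example, assuming V = 10 May**

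| Recorded date | Row 1 | Row 2, month kept | Row 2, literal |
|---|---|---|---|
| Stop: July, day unknown | 10 May | 31 July | 31 December |
| Start: April, day unknown | 10 May, On-treatment | 1 April, pre-study | 1 January, pre-study |

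For an SAE starting on 10 May and ending on an unknown day in July, counting both end days:

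- Row 1: 10 May to 10 May = 1 day.
- Row 2, month kept: 22 + 30 + 31 = 83 days.
- Row 2, literal: 22 + 30 + 31 + 31 + 30 + 31 + 30 + 31 = 236 days.
- Possible values: from 22 + 30 + 1 = 53 days (1 July) to 83 days (31 July).

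Row 1 and the literal reading of row 2 both fall outside the possible range. Row 2 with the month kept gives its upper end.

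**Impossible records under row 1.** A start in April with the day unknown and a known stop of 27 April gives a start of 10 May, which is 3 + 10 = 13 days after the stop. If both days in April are unknown, the start is 10 May and the stop 30 April.

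**Where the rows agree.** If the recorded start month is the month of V, both give V.

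**How much of the pre-visit window is exposed.** Assume a full 30-day gap, onset uniform over the 31 dates from 0 to 30 days before V, and V equally likely on any day of a 365-day year. If V is day d of its month, 31 − d of those dates fall in an earlier month. This sums to 465 for each 30- or 31-day month and 462 for February. The share is (11 × 465 + 462) / (365 × 31) = 5,577 / 11,315 = 49%. It is smaller with shorter gaps, and none is exposed when consent and Visit 1 fall on the same day.

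**The case against.** A reader might infer that SAE stop dates will be displayed wrongly, or that SAE duration and phase will be wrong in general. The documents do not support that.

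- Only dates with a missing day are touched.
- SAP 11.6.2.1 says that listings show the partial date as recorded, so July would appear as July. Protocol 10.4.2 also calls for narratives of deaths and SAEs.
- No planned AE table names duration or time to onset in its title. The layout of the AE listing is not in the documents, so whether a derived duration appears there is unknown.
- SAE tables 3.04 and 3.06 carry no phase restriction in their titles, so an SAE would be counted there under either row.
- Non-serious AEs are collected only from randomisation. Protocol 9.2.1 sends medical occurrences between consent and treatment to the medical history pages, and it requires SAEs to be reported within 24 hours. The phase error is therefore mainly confined to SAEs between consent and Visit 1, in an earlier calendar month, with an unknown start day.
- Row 2 applies only after a query has failed, which will resolve some cases.

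All of this stands as a limit on size, but the contradiction remains. Row 1 is not restricted to dates awaiting a query, so the two rows still overlap once the query fails. The SAP also plans for pre-treatment events: section 9.2.1.1 has the listings identify events during screening, and the All Subjects Enrolled population provides for SAEs between consent and the planned screening visit.

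**Conclusion.** The point holds as a minor one. SAP 11.6.2.1 gives two overlapping, conflicting rules with no precedence. Row 1 is a stated rule that produces wrong results in a one-day study: it conflicts with the phase definitions in Appendix 3 and can place a start after a known stop. Row 2 is closer to what is needed, but it relies on an undefined anchor and, read literally, discards a known month.

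The effect is confined to derived duration or time to onset and to phase-based AE outputs, for events with a missing day. Few events can be expected in a single-visit placebo-device study, and no efficacy analysis is affected. The example rests on an assumed Visit 1 of 10 May; the general result for row 1 does not depend on that date.

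**What to change.** Replace both rows with one rule, before Database Freeze:

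1. Query partial AE dates first.
2. Keep the recorded month and year. A missing start day becomes the first of that month; January is used only if the month is also missing.
3. Move the imputed start to the Visit 1 date only if the recorded period includes Visit 1 and the known or imputed stop date is not before Visit 1. The second condition is needed: with Visit 1 on 10 May, a start in May with the day unknown and a known stop of 5 May would otherwise begin five days after it ended.
4. A missing stop day becomes the last day of the recorded month; December is used only if the month is also missing. Do not cap at treatment stop.
5. Retain the statement that completely missing dates stay missing. It now stands in row 1, so simply deleting that row would lose it.
6. Replace Week 1 Day 1 with the Visit 1 date.

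The cost is SAP wording and the matching derivation code. No new data and no protocol change are needed.
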